9.4.2 Statistical model, hypothesis, and method of analysis

The aim is to estimate the treatment effect of the investigational drug (EMA401) compared to placebo, for the target population on the primary pain parameter. The definition and the justification of the corresponding primary estimand, as well as the definition of the supplementary and secondary estimands are detailed in an Estimand Charter.

The primary estimation method is based on an Analysis of Covariance (ANCOVA) model including region (e.g. US, EU), treatment, sex, use of concomitant pain medication for PHN (yes/no) as factors and baseline (mean pain intensity) score and age as covariates. The analysis will account for different post-randomization events as follows:

- **Changes in doses of concomitant medication for PHN:** Efficacy observations collected during the period of changes in doses of concomitant medication for PHN (compared to

baseline) and the 2-days thereafter will be excluded, since they are considered affected by the concomitant medication dose change. The resulting missing data after this step will be multiply imputed using the Missing at random (MAR) assumption.

- **Intake of rescue medication:** Efficacy data collected during intake of rescue medication will be used for analysis.
- **Intake of prohibited medications with potential confounding effect prior to study treatment discontinuation:** The prohibited medications with a potential confounding effect are defined as those listed in [Table 5-2](#) requiring study treatment discontinuation. Efficacy observations collected during the intake period of such prohibited medications and the 7-days thereafter will be excluded, since they are considered affected by the prohibited medication intake. The resulting missing data after this step will be multiply imputed using the MAR assumption.

The design feature of retrieved drop-outs, considered in order to minimize the occurrence of missing data on primary pain parameter, is exploited for the statistical analysis as follows:

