2.5.2 Statistical hypothesis, model, and method of analysis

The aim is to estimate the treatment effect of the investigational drug (EMA401) compared to placebo, for the target population on the primary pain parameter. The definition and the justification of the corresponding primary estimand, as well as the definition of the supplementary and secondary estimands are detailed in the Estimand Charter.

The primary estimation method is based on an Analysis of Covariance (ANCOVA) model including region (America or Europe and Australia, Asia), treatment, sex, use of concomitant pain medication for PHN (yes/no) as factors and age and baseline (mean pain intensity) score as covariate. The analysis will account for different intercurrent events (i.e. events that occur post-randomization) as follows:

- **Changes in doses of concomitant medication for PHN:** Efficacy observations collected during the period of changes in doses of concomitant medication for PHN (compared to baseline) and the 2-days thereafter will be excluded, since they are considered affected by the concomitant medication dose change. The resulting missing data after this step will be multiply imputed using the Missing at random (MAR) assumption.
- **Intake of rescue medication:** Efficacy data collected during intake of rescue medication will be used for analysis.

- **Intake of prohibited medications with potential confounding effect prior to study treatment discontinuation:** The prohibited medications with a potential confounding effect are defined as those listed in Table 2-1 requiring study treatment discontinuation. A list of prohibited medications is available at the following [REDACTED]

[REDACTED] Efficacy

observations collected during the intake period of such prohibited medications and the 7-days thereafter will be excluded, since they are considered affected by the prohibited medication intake. The resulting missing data after this step will be multiply imputed using the MAR assumption.

Table 2-1 Prohibited medication

Medication	Prohibition period	Action taken for study treatment
Prohibited prior to Randomization and throughout study		
High dose capsaicin patch (8%)	3 months prior to Randomization and after Randomization	Discontinue study treatment
Prohibited 2 week prior to Randomization and throughout the study		
Any skeletal muscle relaxant (e.g. baclofen, orphenadrine, methocarbamol)	2 weeks prior to Randomization and after Randomization	None

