Any change to a different standard of care medication from baseline (e.g. switch from pregabalin to gabapentin) will be treated as prohibited medication	After randomization	Discontinue study treatment

Retrieved drop-out (RDO) patients are defined as patients who discontinue study treatment and decide to remain in the study by following an abbreviated schedule of assessments. These patients must continue to adhere to protocol requirements (see respective protocol Table 6-2). The design feature of retrieved drop-outs, considered in order to minimize the occurrence of missing data on primary pain parameter, is exploited for the statistical analysis as follows:

- **Permanent discontinuation of study treatment due to AE, lack of efficacy (LoE) and use of prohibited medication:** If retrieved drop-out data are available, these will be used for analysis. If no data was retrieved after study treatment discontinuation, missing data

will be multiply imputed based on placebo arm data, i.e. “jump to reference” (J2R) assumption for the EMA401 arms, missing at random assumption for placebo arm (Carpenter, Roger, and Kenward 2013). If no RDO data was collected after study treatment permanent discontinuation, missing data will be multiply imputed based on the J2R assumption for the EMA arms and under the MAR assumption for placebo arm. Of note, alternatively one could build the imputation model based on the RDO data, however, we expect sparse RDO data which will likely hinder us to build an imputation model. More details on the imputation model are specified in Section 5.

- **Permanent discontinuation of study treatment due to other reasons than AE, LoE and use of prohibited medication (including discontinuation due to USM):** If efficacy data collected after study treatment discontinuation are available (retrieved drop-out), then the retrieved drop-out data will be excluded and missing data after study treatment discontinuation will be multiply imputed using the MAR assumption.

The multiple imputations will be carried out on the weekly mean pain score. Details on multiple imputation can be found in Section 5 of this document.

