2.5.3 Handling of missing values/censoring/discontinuations

Handling of missing daily pain score values within a week (within-week imputation)

The 24-hour average pain score is measured daily for seven consecutive days prior to randomization and then every day through the end of the study. At each week, the weekly mean of the seven 24-hour average pain assessments will be calculated.

The weekly mean will be calculated based on the available assessments. If only one measurement is available, the mean will be based on that value. Assessments made under treatment will not be mixed up with RDO data. If there is at least one value among the seven values in one week which is on-treatment (i.e. collected prior to study treatment discontinuation), the mean will be calculated based on those on-treatment values. If all seven values in one week are off-treatment because collected after study treatment discontinuation (RDO), the resulting weekly average will be regarded as an RDO value for analysis.

Handling of missing weekly mean pain score values (weekly mean imputation)

The multiple imputation for the primary variable will be carried out on the weekly mean pain score.

The imputation procedure related to primary analysis is described in Section 2.5.2 while the imputation procedure for the supplementary analyses is included in Section 2.5.4. The details of these imputation rules are specified in the Estimand Charter and in Section 5.

For all analyses, imputation of intermittent missing observations before treatment discontinuation will be carried out following a MAR mechanism for all treatment arms.

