5.1.5 Prohibited medication for PHN

Exclusion period of values in case of changed PHN medication or intake of prohibited medication will be derived as follows:

- Programming Dataset Specification (PDS) will describe how to identify dose changes of concomitant PHN medications and prohibited medications
- determine exclusion period: CM end date + x days where $x=3$ for changes in dose and $x=7$ for intake of prohibited medications with potential confounding effect
- if no medication end date available, then all values from medication start date onwards should be excluded

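### SAP 5.1.5 excludes 3 days after a PHN dose change where SAP 2.5.2 and Protocol 9.4.2 say 2, and does not repeat the 2.5.2 limit of the prohibited-medication exclusion to intake before treatment discontinuation

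*SAP*

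**What the plan says.** SAP 2.5.2 sets the rule for PHN dose changes: "observations collected during the period of changes in doses of concomitant medication for PHN (compared to baseline) and the 2-days thereafter will be excluded". Protocol 9.4.2 has the same rule: "baseline) and the 2-days thereafter will be excluded, since they are considered affected by the concomitant medication dose change". In both documents the gaps are then imputed under missing at random (MAR).

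For prohibited medication, SAP 2.5.2 and Protocol 9.4.2 exclude the intake period and the 7 days after it. Both put this rule under the label "Intake of prohibited medications with potential confounding effect prior to study treatment discontinuation".

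For patients who stop treatment permanently because of an adverse event (AE), lack of efficacy (LoE) or prohibited medication, SAP 2.5.2 says: "If retrieved drop-out data are available, these will be used for analysis". SAP 2.5.3 adds that when a whole week is off treatment, "the resulting weekly average will be regarded as an RDO value for analysis".

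SAP 5.1.5 then derives the windows: "determine exclusion period: CM end date + x days where $x=3$ for changes in dose and $x=7$ for intake of prohibited medications". It also says: "if no medication end date available, then all values from medication start date onwards should be excluded". It does not mention treatment discontinuation.

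**The concern.** SAP 5.1.5 is the text a programmer would use to decide which diary scores enter the weekly means. It differs from the rule it is meant to implement in two ways.

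First, its dose-change window is one day longer than the window in SAP 2.5.2 and the protocol.

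Second, it drops the limit on the prohibited-medication rule. Take a patient who stops for LoE, stays in follow-up and then starts a prohibited analgesic. SAP 2.5.2 uses the later scores. SAP 5.1.5, taken alone, removes them, and removes every one from the start date if no end date is recorded. The situation is foreseeable: Protocol 5.6.2 wants patients who stop to receive best standard of care and to be encouraged to remain in the study.

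At stake are observed Week 12 scores for the primary endpoint, in a group where the SAP already says "we expect sparse RDO data which will likely hinder us to build an imputation model". The direction depends on the patient. If a deleted score is worse than the value imputed for it, deletion flatters EMA401; if it is better, deletion works against EMA401. The responder analysis (SAP 2.7.2) uses the same imputed data.

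**Working it through.** **1. Can day counting reconcile the windows?** The rule texts (SAP 2.5.2, Protocol 9.4.2) give 2 and 7 days after the end date. SAP 5.1.5 gives end date + x with x = 3 and x = 7.

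- If day end + x is itself excluded, 5.1.5 gives 3 and 7 days.
- If exclusion stops the day before, it gives 2 and 6 days.

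Neither convention gives 2 and 7. With x = 2 and x = 7, the first convention does.

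**2. Is it a declared change?** SAP Section 4 does not list it. The SAP amendment table's entry for 5.1.5 says only that the PD date cannot be used. Neither mentions a third day or a dropped limit.

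**3. Inputs for size.**

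- 129 patients were randomized 1:1:1 over three arms (SAP Amendment 1 and 1.1). Assuming equal arms, n = 129/3 = 43.
- SD is 2.0 to 2.6 (SAP Section 3).
- Mean changes are -2.29 on EMA401 and -1.60 on placebo (study EMA401-003, Protocol 3.3.1).
- Standard error of a difference = SD × √(2/43) = 0.43 (SD 2.0) to 0.56 (SD 2.6).

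The number of affected patients is not in the documents and is an assumption.

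**4. The extra day.** Assume a full diary, a dose that returns to baseline, and a third day that falls in Week 12. If m Week 12 days remain under the 2-day rule, and the third day differs by d from the mean of the others, dropping it shifts the weekly mean by d/m. With d = 1:

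- m = 7: 1/7 = 0.14 for the patient; 0.14/43 = 0.003 on the arm mean.
- m = 2: 1/2 = 0.50 for the patient; 0.50/43 = 0.012 on the arm mean.
- m = 1: no day is left and the week changes from observed to imputed. A window can cover all 7 days once the dose-change episode lasts 4 days with x = 3 (4 + 3 = 7), against 5 days with x = 2 (5 + 2 = 7).

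**5. The missing limit.** Let *obs* be the retrieved change from baseline of an EMA401 patient. Gap = obs − imputed value. With k such patients, keeping the scores instead of deleting them shifts the EMA401 − placebo difference by k × gap/43. Two imputations are possible for a deleted score:

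- MAR: imputed = -2.29 + s × (obs + 2.29). Here s is the assumed carry-over from the patient's earlier scores, taken as 0 or 0.7.
- Jump to reference (J2R), which 2.5.2 prescribes when nothing was retrieved after such a stop: imputed = -1.60, with no carry-over.

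Each cell gives the gap per patient, then the shift for k = 3.

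| obs | MAR, s = 0 | MAR, s = 0.7 | J2R |
|---|---|---|---|
| 0 (back at baseline) | 2.29; +0.160 | 0.687; +0.048 | 1.60; +0.112 |
| -1.60 (placebo mean) | 0.69; +0.048 | 0.207; +0.014 | 0; 0 |
| -3.29 (1 point better than arm mean) | -1.00; -0.070 | -0.30; -0.021 | -1.69; -0.118 |

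For k = 0 the shift is zero; for k = 1 it is a third of the tabled value. Over k = 0 to 3 and both imputations the range is about -0.12 to +0.16. One patient can move an arm's responder rate by at most 1/43 = 2.3 percentage points.

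**The case against.** The best defence is that 5.1.5 only derives dates while 2.5.2 sets the scope. The words that follow the quoted window in 5.1.5 repeat the term for confounding prohibited medications that 2.5.2 defines under its pre-discontinuation label, so 5.1.5 need not restate the limit. Identification of dose changes and prohibited medications is left to the Programming Dataset Specification, and imputation detail also sits in the Estimand Charter; neither document was available. Much of this stands. The missing limit is an omission that becomes a conflict only if 5.1.5 is applied literally. The defence does not touch 3 versus 2: 5.1.5 sets that number itself.

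A reader might go further and infer that when a patient is stopped for prohibited medication and keeps taking it, 2.5.2 clearly retains the scores, so that the window must end on the discontinuation date. The documents do not settle this. The label in 2.5.2 can mean intake that began before the stop, in which case its own exclusion of the intake period and the following 7 days may run past it. The retrieved-data bullet points the other way. The same tension is in Protocol 9.4.2, so 5.1.5 did not create it.

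The affected group may also be empty. Patients in follow-up must still observe the prohibited-medication rules (Protocol Section 6), retrieved data are expected to be sparse, and stops under the urgent safety measures are unaffected because their retrieved data are excluded anyway. The table models EMA401 patients only; affected placebo patients could partly cancel the shift.

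**Conclusion.** The 3-day window is a definite error against both SAP 2.5.2 and Protocol 9.4.2. The missing limit is a real but weaker gap. It bears clearly only on prohibited intake that starts after a stop for AE, LoE or prohibited medication, and only if 5.1.5 is applied as it stands.

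Both effects are small beside the standard error: the extra day is negligible unless it empties Week 12, and the largest cut-off shift (0.16) is well under half of the smaller standard error (0.43). These sizes rest on assumed patient counts, equal arms, the earlier study's means and the assumed carry-over. The case for acting is that the rule decides which observed primary scores are used and should be unambiguous before unblinding. The size of the likely bias is not the reason.

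**What to change.** In SAP 5.1.5:

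- Change x=3 to x=2 for dose changes.
- State that the prohibited-medication exclusion, including the rule for a missing end date, applies only to intake that starts before permanent study treatment discontinuation.
- For intake that began before the stop and continues past it, follow the Estimand Charter and cite it there, so that the choice is not left to programming.

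The cost is one number, one clause and one cross-reference before database lock. It needs no new data and no protocol amendment. The first two edits bring 5.1.5 back to the protocol's own rule and add no imputation.

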5.2 AEs coding/grading

The MedDRA version which will be available at the time of database lock, will be used for the coding purpose of the adverse events.

5.3 Laboratory parameters derivations

Liver events defined by laboratory parameter abnormalities (additional non-lab criteria as provided in the protocol are covered under the adverse events analysis, safety topics of interest):

- ALT or $AST > 5 \times ULN$
- $ALP > 2 \times ULN$
- $TBL > 2 \times ULN$
- ALT or $AST > 3 \times ULN$ and $INR > 1.5$
- ALT or $AST > 3 \times ULN$ and $TBL > 2 \times ULN$ AND $ALP \leq 2 \times ULN$ (Potential Hy's Law cases)

- ALT or AST > 3 × ULN

Renal events defined by laboratory parameter abnormalities (additional non-lab criteria as provided in the protocol are ignored):

- Serum creatinine increase 25 – 49% compared to baseline
- Serum creatinine increase ≥ 50% compared to baseline
- New dipstick proteinuria ≥1+
- New dipstick glycosuria ≥1+ not due to diabetes
- New dipstick hematuria ≥1+ not due to trauma
- Albumin- or Protein-creatinine ratio increase ≥2-fold
- Albumin-creatinine ratio (ACR) ≥30 mg/g or ≥3 mg/mmol
- Protein-creatinine ratio (PCR) ≥150 mg/g or >15 mg/mmol

Laboratory results will be reported in SI units.

5.4 Derivation of index values and scores

For details on handling of missing items and derivation of scores refer to the note to file at [path](#)

5.4.1 11-point Numeric Rating Scale (NRS)

The Numeric Rating Scale (NRS) is an 11–point scale for patient self-reporting of pain. The averaged score will be computed for every week, regardless of visits.

24-hour Average Pain Score

The 24-hour average pain score will be assessed using the 11-point numeric rating scale (NRS) scale ranging from zero to ten.

24-hour Worst Pain Score

The 24-hour worst pain score will also be assessed using the 11-point NRS scale ranging from zero to ten.

5.4.2 Verbal Rating Scale (VRS) pain intensity

The Verbal Rating Scale (VRS) is a questionnaire administered by the clinician to capture the patient's level of pain. The response will be recorded as 0 = none, 1 = mild, 2 = moderate, and 3 = severe. The score is recorded at baseline only.

5.4.3 Brief Pain Inventory- Short Form (BPI-SF)

Patients will be asked to complete the 7-item pain interference scale which assesses the degree to which pain interferes with walking and other physical activity, work, mood, relations with others and sleep using a zero to ten numeric rating scale, with zero being "does not interfere" and ten being "completely interferes". The score is recorded at Visits 101, 104, 106, 199, TD visit.

The BPI interference total score will be derived as the sum of the 7 responses for the questions 9A-9G. The total score ranges from 0 to 70.

5.4.4 Patient Global Impression of Change (PGIC)

The Patient Global Impression of Change (PGIC) is a patient-reported instrument that measures change in overall status on a scale ranging from one ("very much improved") to seven ("very much worse"). The score is recorded at Visit 199 and TD visit only.

5.4.5 Neuropathic Pain Symptom Inventory (NPSI)

The Neuropathic Pain Symptom Inventory (NPSI) is a 12 item patient reported outcome measure that contains 10 descriptors representing 5 dimensions of pain (burning pain, deep/pressing pain, paroxysmal pain, evoked pain and paraesthesia/dysesthesia) and 2 temporal items designed to assess pain duration and the number of pain paroxysms. The score is recorded at Visits 101, 104, 106, 199, 201 and TD visit.

The sum of the responses to the 10 questions (all except qn. 4 and qn. 7) will be regarded as the total score and will be used for the analysis.

[figure not shown]
The dimensional score of each of the five dimensions are calculated as follows :

[figure not shown]
[figure not shown]
[figure not shown]
- Burning = Q1
- Pressing = (Q2 + Q3) /2
- Paroxysmal = (Q5 + Q6) /2
- Evoked = (Q8 + Q9 + Q10) /3
- Paraesthesia / dysesthesia = (Q11 + Q12)/2

[figure not shown]
5.4.6 Insomnia Severity Index (ISI)

Patients will be asked to complete the ISI using five-point Likert-style scale as a measure of perceived sleep difficulties. Scores can range from zero to 28, with a cut-off score of eight suggesting the presence of sub-threshold insomnia. The questionnaire assesses the severity of insomnia, satisfaction with current sleep pattern, sleep interference, "noticeability" of sleeping problem to others and concern about sleeping problems. The score is recorded at Visits 101, 199 and TD visit.

The sum of seven responses represents the total score. Each of the 7 items is scored using a range from 0 to 4, thus the total score values can range from zero to 28.

5.5 Statistical models

SAS codes for all statistical methodology described in this section will be included as programming note in TFL Shells.

5.5.1 Primary analysis

5.5.1.1 ANCOVA

The primary analysis (and all other analyses of continuous variables) will be done using analysis of covariance. The model is:

mean pain score = intercept + region + treatment + sex + age + PHNmed (yes/no) + baseline (mean pain intensity) + error.

The SAS procedure MIXED will be used for computing p-values and 95% confidence intervals for LS means.

5.5.1.2 Missing data imputation

For the purpose of missing data imputation, the following two scenarios will be considered:

- Jump to reference (J2R)
- Missing At Random (MAR)

The imputation will be based on all available data (i.e. from all scheduled time points) using all covariates as specified in the ANCOVA model. For J2R only placebo data will be used, for MAR data from the same treatment arm will be used for building the imputation model.

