If the 300 mg b.i.d dose would have been initiated: The primary objective would have been achieved if the null hypothesis of flat dose-response curve (where all dose means are equal to the placebo mean) at Week 12 is rejected using $\alpha=0.025$ one-sided. The null hypothesis of a flat dose-response curve will be tested using Multiple Comparison Procedure – Modelling (MCP-Mod) with three E_{\max} and two sigmoidal- E_{\max} dose response models as the candidate shapes. The following ED_{50} (the dose at which half of the maximum effect is reached) values will be used for the E_{\max} models: 17, 80, and 200. The parameters of the sigmoidal E_{\max} models (ED_{50} , h) will be as follows: (77, 3) and (175, 1.5), where h is the Hill parameter that determines the steepness of the dose-response shape. The MCP-Mod dose response test will be performed at each post-baseline visit. No multiplicity adjustment by visit will be carried out.

Dose-response estimation will be performed based on the ANCOVA least square estimates using MCP-Mod as described in Pinheiro et al (2014). The same candidate models as above will be used in a model averaging approach to obtain an estimate of the dose-response curve. The final estimate of the dose-response curve is the median of the dose-response curves obtained.

The same ANCOVA model will be applied at the visits prior to Week 12.

Summary statistics for absolute values and change from baseline by treatment and visit will be provided for the original measurements (i.e. the raw data prior to multiple imputation) of the primary efficacy variable. If a measurement is collected under the period of use of prohibited medications or the 7 days thereafter, it will be excluded from the summaries. [REDACTED]

In the event the EMA401 300 mg b.i.d. dose cannot be initiated, the trend tests deduced from the set of candidate models will be performed but the dose response estimation will not be performed. In that case, the first secondary objective will be evaluated to compare the efficacy of the remaining doses of EMA401 over placebo in 24-hour average pain intensity score at Week 12, using an 11 point Numeric Rating Scale (NRS). This comparison will be done by

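### SAP 5.5.1.2 builds the jump-to-reference model from placebo data only; followed as written, this gives copy-reference, not the method named in SAP 2.5.2

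*SAP*

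**What the plan says.** SAP 2.5.2 treats three reasons for stopping (adverse event, lack of efficacy, prohibited medication) alike. Retrieved data come first: "If retrieved drop-out data are available, these will be used for analysis". Where there are none, the rule is "J2R) assumption for the EMA401 arms, missing at random assumption for placebo arm", with a citation to the reference-based imputation framework and a pointer to Section 5. Stops for "other reasons than AE, LoE and use of prohibited medication (including discontinuation due to USM") are imputed under MAR.

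The only model detail in Section 5 is in SAP 5.5.1.2. On predictors it says "The imputation will be based on all available data (i.e. from all scheduled time points) using all covariates" of the ANCOVA model. On the source of the model it says "For J2R only placebo data will be used, for MAR data from the same treatment arm will be used for building the imputation model". Own-arm data are therefore assigned to MAR and kept out of J2R.

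Two further sources are named but were not available. SAP 2.5.3 says "The details of these imputation rules are specified in the Estimand Charter and in Section 5", and SAP 5.5 says "SAS codes for all statistical methodology described in this section will be included as programming note in TFL Shells".

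**The concern.** J2R and copy-reference share the same post-stop placebo means. They differ in how a patient's on-drug weeks enter. J2R takes them as residuals from the patient's own arm, so an average EMA401 stopper is imputed at the placebo mean. Copy-reference takes them as residuals from placebo, so a patient who was better than placebo while on drug is imputed as a placebo patient who happened to be doing well.

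Protocol 3.2 wants these stops to count against the drug. Protocol 9.4.4, in the first supplementary analysis, ties jump to reference to a stopper having no advantage over placebo. Copy-reference leaves an advantage in the primary Week 12 difference. The responder analysis (SAP 2.7.2) and the NPSI analysis (SAP 2.7.3) use the same imputation.

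The remaining supportive analyses would not reveal it. SAP Section 4 drops the tipping-point analysis and the first and third supplementary analyses. The supplementary analysis that is kept uses MAR for all stops, and the mFAS sensitivity analysis reuses the primary rules.

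**Working it through.** **Plan's own figures.** No figure in either document depends on this choice. The stated power of at least 77% reproduces: the minimum over the five candidate shapes is 77.2% with doses in mg per administration and 76.7% with daily mg. It is not in dispute.

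**The two rules.** Write P for placebo, A for the EMA401 arm, and B for the placebo regression of Week 12 on the observed history.

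- J2R: mu_P,post + B(y_pre − mu_A,pre)
- Placebo-only model fed the patient's own scores: mu_P,post + B(y_pre − mu_P,pre)
- Mean gap: B(mu_A,pre − mu_P,pre)

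The gap is zero if the arms do not differ before the stop. Otherwise it favours EMA401 whenever the arm showed early benefit.

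**Inputs from the documents.**

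- Effect at 100 mg b.i.d.: 2.29 − 1.60 = 0.69 points at four weeks (Protocol 3.3.1).
- SD 2.6 (SAP Section 3).
- 129 patients randomized (SAP Amendment 1).
- Five candidate shapes (SAP 2.5.2).

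**Assumptions, because the documents are silent.**

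- Weekly means are exchangeable with correlation 0.3 to 0.8, or AR(1) with 0.7 to 0.95.
- The effect rises linearly to Week 4 and then stays constant.
- Baseline is in the history, as it is an ANCOVA covariate.
- Stops are spread evenly over Weeks 2 to 10.
- There are 43 patients per arm (129/3).

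**Two cases that can be checked by hand.**

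- Exchangeable 0.5, stop after Week 8: each coefficient is 0.5/(1 + 8 × 0.5) = 0.10. The on-drug differences sum to 0.69 × (0.25 + 0.5 + 0.75 + 5 × 1) = 4.485. Carry = 0.10 × 4.485 = 0.448.
- AR(1) 0.9, stop after Week 4: only the last week counts. Carry = 0.9^8 × 0.69 = 0.297.

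Simulation with 200,000 patients per arm gave 0.456 and 0.295 for these cases under the literal rule, and 0.000 with own-arm centring.

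**Mean carry over stops at Weeks 2 to 10 (effect 0.69).**

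| Correlation | Carry, points |
|---|---|
| Exchangeable 0.3 / 0.5 / 0.8 | 0.305 / 0.354 / 0.391 |
| AR(1) 0.7 / 0.8 / 0.9 / 0.95 | 0.118 / 0.206 / 0.360 / 0.477 |

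As a share of the effect this is 0.118/0.69 = 0.17 to 0.477/0.69 = 0.69. By timing, a Week 4 stop carries 0.04 to 0.46 points and a Week 8 stop 0.17 to 0.56.

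**Shift in the 100 mg b.i.d. difference** = share imputed × mean carry. The pairwise SE is 2.6 × sqrt(2/43) = 0.56.

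| Share of arm imputed (assumed) | Overstatement, points | Largest, in SE |
|---|---|---|
| 5% | 0.01–0.02 | 0.04 |
| 10% | 0.01–0.05 | 0.09 |
| 20% | 0.02–0.10 | 0.17 |
| 30% | 0.04–0.14 | 0.26 |

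**25 mg b.i.d.** The candidate shapes give its effect as a fraction of the 100 mg effect. The SAP does not state the unit of the ED50 values, so both scales are shown, in the order Emax 17, 80, 200, then sigmoid (77, 3), (175, 1.5).

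- Per-dose mg: 0.696, 0.429, 0.333, 0.048, 0.170.
- Daily mg: 0.810, 0.538, 0.400, 0.227, 0.241.

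At 30% imputed the overstatement is at most 0.30 × 0.477 × 0.696 = 0.10 points (0.18 SE) on the per-dose scale, or 0.30 × 0.477 × 0.810 = 0.12 points (0.21 SE) on the daily scale. At the low end it is under 0.01.

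**Outside these assumptions.** AR(1) 0.5 carries only about 0.055 of the effect, so 0.30 × 0.055 × 0.69 = 0.01 points at 30%. Full effect from Week 1 with high exchangeable correlation gives about 0.17 at 30%. If baseline is also left out of the history, a Week 4 stop with exchangeable correlation 0.5 to 0.9 gives 0.16 to 0.21.

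**The case against.** The strongest reply is that SAP 5.5.1.2 says which arm's data build the model, not how on-drug weeks are centred. It still calls the method jump to reference, so the line may be shorthand. If on-drug weeks were not predictors at all, the imputed mean would be the placebo mean and the copy-reference label would not apply. The Charter or the code may settle it. This stands as a limit on what can be claimed about the analysis actually run. It does not rescue the text: the section points to all scheduled time points and reserves own-arm data for MAR, so a programmer who follows it has no own-arm means to subtract.

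The reach is also narrow. Retrieved data take precedence, Protocol 5.6.2 plans follow-up after stopping, and USM stops, of which the SAP says there are many, go to MAR. All of this is right. SAP 2.5.2 does say that retrieved data are expected to be sparse. That makes imputation more likely for the stops in question, but it gives no rate and could also mean few such stops.

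A patient stopping for lack of efficacy may have had no benefit to carry. For that patient the literal rule imputes roughly placebo and J2R imputes worse than placebo. The gap between the methods is unchanged, since it depends on arm means, but retained benefit is then the wrong description.

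Finally, the sizes are not bounds. They move with the assumed correlation, onset and share imputed, as the last cases in the working show.

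**Conclusion.** The point holds. SAP 2.5.2 names one method, and the only rule given for carrying it out produces another, in EMA401's favour if the drug works. This is a conflict in the SAP text, not proof that the wrong analysis was run. Under the listed assumptions 0.17 to 0.69 of the on-drug effect is carried to Week 12 per imputed patient, where J2R would carry none on average. The effect on the arm difference is a fraction of a standard error even at 30% imputed. The true share of patients affected is unknown. Under a flat dose-response the carry is zero, so the one-sided 0.025 level is untouched by this route. It should be fixed because it concerns the primary estimand and the fix is cheap, not because the number is large.

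**What to change.** In SAP 5.5.1.2, state that under J2R the pre-discontinuation residuals are taken from the patient's own-arm means, while the post-discontinuation means and the regression of later on earlier weeks come from placebo. If copy-reference is what is intended, rename the method in both 2.5.2 and 5.5.1.2. In either case confirm that the Estimand Charter and the imputation code agree with the SAP.

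The cost is one sentence and, only if the code follows the literal text, a change to the imputation program. No sample size or power figure changes. If there is a drug effect, correcting literal code makes the estimate slightly less favourable to EMA401.
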